## Mastectomy Flap Temperature and Clinical Implications

Wake Forest Baptist Comprehensive Cancer Center

WFBCCC # 74222

## 5.0 Study Design and Study-Related Activities

### 5.1 Design

- This is a prospective observational (non-randomized) study that will collect data intraoperatively and assess exploratory outcomes up to 90 days post-surgery through chart review
- Information that will be stored within a secure database will include demographic data, details of medical, surgical, and social history, oncologic history, and surgical data surrounding the mastectomy and reconstruction until 90 days post operatively through chart review. The only piece of identifying data that will be collected is the medical record number in order to allow prospective chart review for the surgical outcome measurements.

All patients of the age of 18 or above that are scheduled for mastectomy and implant-based breast reconstruction and who meet our remaining eligibility requirements will be screened for our study and enrolled if they consent. If the patient meets eligibility requirements a study team member will reach out to them via a telephone call prior to their surgery date. If the patient expresses an interest in taking part in the study a study team member will meet with them in the pre-op holding room the day of surgery to obtain written informed consent. To address our feasibility objectives, we plan to record the medical record numbers of patients who decline participation in the study. Clinical data and patient information will be entered into an encrypted, password protected database by approved study personnel. The type of information that will be collected and entered into the database will include (but not be limited to) that shown below in Table 1. The database will be updated with pertinent information for each subject after each surgery and postoperative visit on an intermittent basis. The intraoperative data points will be collected through the use of a myocardial temperature probe (See Section 6.1.1 and Figure 1) introduced into the 4 quadrants. This is a disposable temperature sensor. One sensor will be utilized for each patient. The flap temperatures will be collected by the research staff. There will be a hard stop on the probe at 4mm of depth in order to assess the temperature of the subdermal plexus upon which the mastectomy flap will be perfused. Core temperature will be assessed simultaneously using standard-of-care anesthesiologist-mediated methods involving a temperature probe placed in the nasopharynx. For this study specifically, core temperatures will be recorded at the same time intervals as the localized mastectomy flap temperatures are obtained.

**OF NOTE:** Due to risk of puncturing the implant with the myocardial temperature sensor post implant placement, flap temperatures at this time point will not be collected. If a pre-implant temperature is missed, post-implant flap temperatures are not allowed.

#### 5.1.1 Smiths Medical Myocardial Temperature Sensor

A myocardial temperature sensor will be used to obtain flap temperatures (Figure 1). The sensor is in a 22 gauge needle and is 8mm in length. This is a disposable temperature sensor. One sensor will be utilized for each patient. The flap temperatures will be collected by the research staff. There will be a hard stop on the probe at 4mm of depth in order to assess the temperature of the subdermal plexus upon which the mastectomy flap will be perfused.

## Mastectomy Flap Temperature and Clinical Implications

Wake Forest Baptist Comprehensive Cancer Center

WFBCCC # 74222

**Figure 1.** Smiths Medical Temperature Probe

### 5.1.2 Temperature-Related Supportive Care

The surgical and anesthesia literature defines 36 degrees Celsius or less as hypothermic and 38 degrees or greater as hyperthermic. These values will also be used for the mastectomy flap temperatures. The mastectomy flap temperatures that are below 36 degrees are considered to be physiologically hypothermic and anything above 38 degrees Celsius is physiologically hyperthermic. However, the standard of care is to only treat the core temperature of the patient, which will be what we adhere to in this study. If the patient is hypothermic standard intraoperative protocols such as increasing the room temperature, turning on the Bair hugger and running warm fluids will be performed to correct hypothermia. If the patient is hyperthermic, running cool fluids, turning off the Bair hugger and decreasing the room temperature will be implemented for correction of hyperthermia.

**Table 1: Data Points to be Collected**

Preoperative	

- MRN

- Age

- BMI

- Smoking status

- Diabetes Mellitus

- Neoadjuvant radiation

- Neoadjuvant Chemotherapy

- Tumor type and stage

Intraoperative	

- Mastectomy weight

- Size of tissue expander or implant placed

- Number of drains placed

- Temperature collection:

- Pre-mastectomy - core temp and flap temp in 4 quadrants

## **Mastectomy Flap Temperature and Clinical Implications**

Wake Forest Baptist Comprehensive Cancer Center

WFBCCC # 74222

	

- Post-mastectomy - core temp and flap temp in 4 quadrants

- Pre-implant placement – core temp and flap temp in 4 quadrants

Postoperative	

- Duration of drains

- Seroma formation

- Infection within 90 days

- Antibiotic administration postoperatively, up to 90 days

- Mastectomy flap necrosis within 90 days

## **Mastectomy Flap Temperature and Clinical Implications**

Wake Forest Baptist Comprehensive Cancer Center

WFBCCC # 74222

### **5.2 Overview of Study-Related Activities**

	Pre-Study	Intraoperatively	Post-Operative Clinic Visit	Up to 90 days post-operatively
Informed consent	X			
Temperature Collection		X		
Demographic Data				X
Chart Review Items				X
Adverse event evaluation (CTCAE v5.0)		X	X	X

## Mastectomy Flap Temperature and Clinical Implications

Wake Forest Baptist Comprehensive Cancer Center

WFBCCC # 74222

### 5.4 Duration of Follow Up

For the purposes of this research study, patients will be followed for 90 days after surgery for adverse events from the introduction of the probe to collect temperature and for exploratory outcomes.

### 5.5 Off-Study Criteria

- The patient completes all study activities, and no further follow-up or data collection is required.
- The patient withdraws from all study activities and further data collection.
- The condition of the patient changes in a manner that it is determined that it is no longer in the patient's best interest to continue the study in the opinion of the investigator.
- Patient lost to follow-up
- Death

## 6.0 STATISTICAL CONSIDERATIONS

### 6.1 General Design Issues

This is a non-randomized prospective observational pilot study.

1. **Primary Hypotheses:** We hypothesize that at least 60% of eligible patients will consent to having flap temperatures measured intraoperatively, and that we will successfully measure all relevant temperatures (12 per breast) on at least 90% of those consenting. Both of these measures must be achieved to deem a future study feasible.
2. **Secondary hypotheses:** We hypothesize that we will observe a significant difference between average mean flap temperature and average core body temperature.
3. **Exploratory analyses:** We will describe post-surgical complications over the 90-day post-surgery period as frequencies.

### 6.2 Sample Size

Our target sample size of 30 eligible patients, expected to be accrued over a period of 3-6 months, is based on our primary goals of examining feasibility measures to inform the design of a larger intervention trial. An n of 30 will provide reasonably tight estimates of our parameters of interest. We will be able to estimate these proportions within 19.4% (for the lower CI bound; the window is smaller for the upper bound) using a two-sided 95% confidence interval. If the consent proportion is below 40.6% (fewer than 12 women consenting out of the 30 eligible), or the success in measuring all flap and peri-incisional temperatures occurs in fewer than 65% of the expected n=18 (i.e., fewer than n=11 women out of the starting pool of 30), we will conclude that a larger study of flap temperatures may not be feasible.

Power calculations for a subsequent larger study will be based on clinically and statistically meaningful differences between average flap temperatures and core body temperatures and will be informed by measures obtained in this pilot.

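### The 19.4-point precision in section 6.2 holds for consent (n = 30) but not for complete measurement, where the expected 18 consenters give a lower window of about 24 points

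*Combined protocol and SAP*

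**What the plan says.** Section 6.2 sets the size of the study with "Our target sample size of 30 eligible patients". It justifies that number by precision: "An n of 30 will provide reasonably tight estimates of our parameters of interest". The figure that follows is put this way: "We will be able to estimate these proportions within 19.4" percent. The text attaches it to the lower limit of a two-sided 95% interval and says that the distance to the upper limit is shorter. No other precision figure is given for either proportion.

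There are two primary proportions, and section 6.1 requires both targets to be met before a larger study is called feasible:

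- **Consent:** the hypothesis is that "at least 60% of eligible patients will consent to having flap temperatures measured intraoperatively". The denominator is eligible patients, planned as 30.
- **Complete measurement:** the hypothesis is that the team will "successfully measure all relevant temperatures (12 per breast) on at least 90% of those consenting". The denominator is consenting patients, and section 6.3 uses the same one.

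Section 6.2 itself supplies the expected size of that second denominator when it sets the lower feasibility floor for measurement at "fewer than 65% of the expected n=18".

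**The concern.** The precision sentence speaks of proportions in the plural and of an n of 30, but only consent has 30 as its denominator. Measurement success will be estimated in a smaller group whose size is not fixed in advance, because it depends on the consent rate. A smaller denominator usually means a wider interval, so a single figure for both proportions needs checking.

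Precision is the only sample-size justification in the plan, and the measurement proportion is one of the two results on which the feasibility conclusion depends. If the figure is too favourable for that outcome, the planned precision is overstated exactly where the data will be thinnest.

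**Working it through.** **Inputs.** Two-sided 95% interval, 30 eligible patients and 18 expected consenters (section 6.2); hypothesised proportions of 60% and 90% (section 6.1). The expected 18 is 0.60 × 30.

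**Formula.** The plan does not name its interval method. For x successes out of n, the exact (Clopper-Pearson) limits are:

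- lower = the 0.025 quantile of Beta(x, n − x + 1)
- upper = the 0.975 quantile of Beta(x + 1, n − x)
- lower window = x/n − lower; upper window = upper − x/n

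**Step 1: reproduce the plan's figure.** For consent, x = 18 and n = 30. The limits are 40.6% and 77.3%.

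- Lower window: 60.0 − 40.6 = 19.4 points.
- Upper window: 77.3 − 60.0 = 17.3 points.

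This matches the stated 19.4, the 40.6% consent floor and the remark that the upper window is smaller. Other methods at 18/30 give lower windows of 17.5 (Wald), 17.7 (Wilson), 17.7 (Agresti-Coull), 17.8 (Jeffreys) and 19.3 (Wilson with continuity correction). Of the methods tried, only the exact one gives 19.4, so it is used below.

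**Step 2: how general 19.4 is at n = 30.** 21/30 also gives 19.4, and the largest lower window for any result with n = 30 is 19.5 (at 19/30 and 20/30). So 19.4 is close to a worst case for any proportion with 30 in the denominator. The question is therefore whether 30 is the right denominator.

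**Step 3: complete measurement with 18 consenters.** 90% of 18 is 16.2, so the nearest attainable result is 16/18.

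| Result | Estimate | Exact lower limit | Lower window |
|---|---|---|---|
| 15/18 | 83.3% | 58.6% | 24.8 |
| 16/18 | 88.9% | 65.3% | 23.6 |
| 17/18 | 94.4% | 72.7% | 21.7 |
| 18/18 | 100% | 81.5% | 18.5 |

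The full interval at 16/18 is 65.3% to 98.6%. Its lower window exceeds the stated one by 23.6 − 19.4 = 4.2 points. Of the results from 9/18 to 18/18, only 18/18 meets 19.4.

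**Step 4: sensitivity to the number of consenters.** If true consent is 60%, the number consenting is Binomial(30, 0.6), with 2.5% and 97.5% quantiles of 13 and 23. Near 90% success:

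| Consenters | Result | Lower window |
|---|---|---|
| 13 | 12/13 | 28.3 |
| 18 | 16/18 | 23.6 |
| 22 | 20/22 | 20.1 |
| 23 | 21/23 | 19.3 |

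About 23 consenters are needed to reach 19.4. The chance of 23 or more at 60% consent is about 4%.

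**Step 5: does another interval method rescue the claim?** At 16/18 the lower windows are 20.0 (Jeffreys), 21.7 (Wilson), 22.9 (Agresti-Coull) and 25.0 (Wilson with continuity correction), all above 19.4. Wald gives 14.5, but Wald is symmetric at 18/30 with a window of 17.5, so it reproduces neither the plan's 19.4 nor its smaller upper window.

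**The case against.** **The gap is small and changes nothing operational.** It is about 4 points, in one planning sentence of a 30-patient observational pilot. Sections 4.1 and 6.3 already require a 95% interval for each proportion, so the final report can show the true precision whatever section 6.2 says. The smaller denominator is visible a sentence later in section 6.2. All of this stands, and it is why the point is a should-fix correction and no more.

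**Success could be counted out of 30.** Section 6.2 also expresses the measurement floor as a count from the starting pool of 30, and 16/30 gives a lower window of 19.0 points, inside 19.4. This does not hold: sections 6.1 and 6.3 define success among consenters, and the 65% floor is a percentage of 18.

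**The sentence might refer to consent alone.** The plural, and the mention of parameters of interest just before it, tell against that. On that reading the second proportion would have no stated precision at all, and the same edit would be needed.

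**Stronger readings that a reader might infer.** One is that section 6.2 demonstrably contradicts itself, because its 65% floor is the lower limit for 16/18. The match with 65.3% is close and suggests that n = 18 was used there, but the plan does not say how 65% was chosen, and a feasibility floor need not be a confidence limit. Another is that the sample size or the feasibility rule must be wrong. That does not follow either: the floor is already stated against 18 consenters, and no required precision is set that 18 would fail to meet.

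**Conclusion.** The precision statement is wrong as written for one of the two primary proportions. It is correct for consent: 19.4 points at 18/30. For complete measurement with the expected 18 consenters, the lower window is 23.6 points at 16/18 (21.7 at 17/18, 24.8 at 15/18). It reaches 28.3 points (12/13) if consenters number 13, the low end of the 95% range.

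This rests on three things: the exact interval, inferred because it reproduces the plan's own figures; consenters as the denominator, as sections 6.1 and 6.3 say; and 60% true consent for the expected 18 and the range of 13 to 23. The direction of the finding does not depend on the exact method, since Wald is the only method tried that falls below 19.4 at 16/18.

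Severity: should-fix. What needs correcting is the stated precision.

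**What to change.** Confine 19.4 to consent and give complete measurement its own figure. Suggested replacement for the precision sentence in section 6.2:

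> Consent (n = 30): 18/30 gives an exact 95% CI of 40.6% to 77.3%, a lower window of 19.4 points. Complete measurement (expected n = 18 consenters): 16/18 gives an exact 95% CI of 65.3% to 98.6%, a lower window of 23.6 points, wider if fewer women consent.

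This also names the interval method. The sentence before it, which credits an n of 30 with tight estimates of all parameters, should be limited to consent or reworded to match.

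The cost is a short text edit and a less favourable stated precision for the second proportion. No extra patients are needed, and the tests and the feasibility rule stay as they are.

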To date there has been no study that has examined the feasibility of objectively quantifying the temperature of mastectomy flaps, or that has studied the relation between flap temperatures and core body temperature. This pilot study seeks to establish foundational evidence related to the feasibility of measuring temperatures of mastectomy flaps and to quantify the relation between flap and core temperatures. Specifically, we hypothesize that 1. we will be able to obtain consent from at least 60% of women undergoing therapeutic or prophylactic mastectomy (unilateral or bilateral, with reconstruction) to obtain flap temperatures intraoperatively, both pre- and post-mastectomy (note that core body temperature is measured continually as a usual aspect of intraoperative procedure, and thus does not require specific additional consent); 2. we will be able to successfully measure flap temperatures in 4 quadrants of relevant breast tissue (one or both breasts, depending on unilateral vs bilateral surgery) at each time point on at least 90% of those who do consent; and 3. average mastectomy flap temperatures will be significantly lower than core body temperature in this pilot sample.

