## **2.0 Objectives**

### **2.1 Primary Objective(s)**

- 2.1.1 Quantify the proportion of eligible women approached who consent to intraoperative (pre and post mastectomy) measurement of mastectomy flap temperatures in each of 4 quadrants of each relevant breast (i.e., unilateral or bilateral procedure).
- 2.1.2 Quantify the proportion of patients upon whom the surgical team is able to obtain intraoperative flap measurements from each of 4 quadrants on each relevant breast pre- and post-mastectomy and pre-implant.

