## **4.0 Study Outcomes and Study Measures**

### **4.1 Primary Outcomes**

5.1.1 The proportion of eligible women who consent to having mastectomy flap temperatures measured during surgery will be computed by dividing the total number of eligible women screened by the number of these women who consent. We will compute a 95% confidence interval around this proportion.

5.1.2 We will compute the proportion who successfully have all relevant flap temperatures measured (this will either be 12 or 24 total expected flap temperatures: 4 quadrants, at three time points- pre and post-mastectomy and pre-implant placement; one or both breasts), and we will compute a 95% confidence interval around this proportion.

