### **6.3 Data Analyses**

This study will provide quantitative data on consent (proportion of all eligible patients approached who consent to having flap temperatures measured intra-operatively), and on ability to successfully measure all 12 flap temperatures (per breast) on patients who have consented.

We will calculate 95% confidence intervals for each of the above feasibility measures to determine the range of estimates that are consistent with our data. We will use one-sample tests of binomial proportions to compare the consent and successful measurement proportions to the hypothesized values of 60% and 90%, respectively.

We will examine intra-individual variability in flap temperature measurements by quadrant and by breast; we expect these sources of potential variability to be weak, controlling for time point of measurement (pre vs post mastectomy vs pre-implantation). We will derive average flap temperatures for each of the three time points separately. We will compare average flap temperatures at each of the three time points during surgery to average core body temperature at that time, using paired t-tests for the differences in means in a single sample. Our hypothesis is that, across all three time points, average flap temperatures will be lower than average core body temperatures, and that as time goes on during surgery, from pre- to post-mastectomy to pre-implantation, we expect average flap temperatures will be lower than average core body temperatures by a larger degree, as we expect flap temperatures to cool more quickly during surgery than overall body temperature.

In our exploratory analyses, we will document the occurrence and major and minor wound/surgical complications over the 90-day period following surgery and will examine whether there is a relation between the number of such complications per patient and 1. the patient's magnitude of difference between average flap temperatures and core body temperatures, and 2. the patient's absolute average flap temperatures .

.

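### The no-go rule in section 6.2 counts peri-incisional temperatures that the protocol does not plan, so its event differs from the primary outcome

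*Combined protocol and SAP*

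**What the plan says.** All references are to the combined protocol and SAP.

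- **Section 6.2 (no-go rule).** A larger study may not be feasible if "the success in measuring all flap and peri-incisional temperatures occurs in fewer than 65% of the expected n=18", glossed as "fewer than n=11 women out of the starting pool of 30".
- **Section 2.1, item 2.1.2 (primary objective).** The proportion of patients on whom the team can "obtain intraoperative flap measurements from each of 4 quadrants on each relevant breast pre- and post-mastectomy and pre-implant".
- **Section 4.1, second item (primary outcome).** Success means that all relevant flap temperatures are measured: "this will either be 12 or 24 total expected flap temperatures: 4 quadrants, at three time points- pre and post-mastectomy and pre-implant placement", for one or both breasts.
- **Section 6.1 (primary hypothesis).** "we will successfully measure all relevant temperatures (12 per breast) on at least 90% of those consenting". The same paragraph requires both this target and the 60% consent target to be met before a future study is called feasible.
- **Section 6.3 (analysis).** The measure is the "ability to successfully measure all 12 flap temperatures (per breast) on patients who have consented".
- **Section 5.1 and Table 1 (data collection).** The probe goes into the four quadrants. At each of the three time points the table lists core temperature and four-quadrant flap temperature, and no other temperature.

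The term peri-incisional occurs once in the supplied text, in section 6.2. No site, time point or number of such readings is given.

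**The concern.** Feasibility is the primary purpose of this pilot, and section 6.2 holds the numerical floor below which the team would conclude that a larger study may not be feasible. That floor is a count of women with a successful measurement, so it means something only once success is defined. Section 6.2 defines it with an extra component that the study does not collect. Every other operative section defines it without that component.

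Whoever applies the rule must therefore decide, without guidance from the plan, what to do about the missing component. They could count it as a failure, ignore it, or start taking extra readings. The first two can give opposite verdicts on the same data. The third would change what is measured after the primary outcome has been fixed.

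**Working it through.** **1. Reproduce the plan's own figures.** Inputs from sections 6.1 and 6.2: 30 eligible women, 60% consent, 90% measurement success, two-sided 95% interval. Expected consenters: 0.60 × 30 = 18.

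The exact (Clopper-Pearson) limits for x successes in n are the 0.025 quantile of Beta(x, n − x + 1) and the 0.975 quantile of Beta(x + 1, n − x).

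| x/n | Exact lower | Exact upper | Wilson lower | Wald lower |
|---|---|---|---|---|
| 18/30 | 40.6% | 77.3% | 42.3% | 42.5% |
| 16/18 | 65.3% | 98.6% | 67.2% | 74.4% |

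- Consent: 60.0 − 40.6 = 19.4 points below and 77.3 − 60.0 = 17.3 above. This matches the stated 19.4% and the remark that the upper side is narrower.
- Measurement: 0.90 × 18 = 16.2, nearest whole number 16. The exact lower limit for 16/18 is 65.3%, which matches the stated 65%.

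The floor therefore appears to come from the 90% hypothesis, which sections 6.1 and 6.3 define on flap readings alone.

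**2. Count the planned readings.** 4 quadrants × 3 time points = 12 for one breast, and 12 × 2 = 24 for two. These are the totals in section 4.1, and the per-breast figure recurs in sections 6.1 and 6.3. Flap readings account for all of them, leaving none to be peri-incisional. Section 5.1 says that the data collected are not limited to Table 1, and the schema figure is not available. Neither affects this count, which is closed.

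**3. Apply the rule under each reading.** Assume that 18 women consent and that outcomes are independent between women.

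*Absent readings count as failures.* Successes = 0 of 18, whatever the flap data show. 0 is below 11, so the rule fires with probability 1. The exact 95% interval for 0/18 runs from 0% to 1 − 0.025^(1/18) = 18.5%.

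*Phrase ignored.* X ~ Binomial(18, p), with success as in section 4.1. The true p is unknown, so a range is shown. The last column uses the percentage floor, since 0.65 × 18 = 11.7 means that 11 also falls below it.

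| True p | P(X < 11) | P(X < 12) |
|---|---|---|
| 0.90 | 0.02% | 0.12% |
| 0.80 | 1.6% | 5.1% |
| 0.65 | 27.2% | 45.1% |

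As an example, suppose 16 of 18 women have every flap reading. The rule does not fire if the phrase is ignored (16 ≥ 11), and fires if the absent readings count as failures (0 < 11).

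**4. Effect of the correction.** The flap-only event leaves 18, 16/18 and 65% as they are. No threshold moves.

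**The case against.** The strongest defence is that the intended event is not in doubt. Four sections and Table 1 agree on flap readings, the 65% floor reproduces from the flap-only hypothesis, and the sentence containing the rule ends by referring to a larger study of flap temperatures. On this view the phrase is leftover wording and an analyst would pass over it. That is probably right about intent, and it supports the correction proposed. It does not make the written rule usable, because the plan nowhere says that the phrase is to be ignored.

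Three stronger readings are tempting, and the documents do not support them.

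- A reader might infer that a no-go verdict is certain. That follows only if an unplanned reading is scored as a failed one. If no peri-incisional readings are planned, the set is empty, and obtaining all flap readings satisfies the condition.
- A reader might infer that section 6.2 is the only feasibility rule. Section 6.1 also has one, tied to 12 readings per breast, and the section 6.2 conclusion is worded softly.
- A reader might infer from section 1.0 a third definition with fewer readings, since it speaks of consent "to obtain flap temperatures intraoperatively, both pre- and post-mastectomy". Those words belong to the 60% consent hypothesis. The 90% hypothesis that follows says only that readings are taken at each time point and gives no number. Pre-implant readings are also taken after mastectomy, so the phrase does not exclude them.

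**Conclusion.** The concern holds in a limited form. The event in the section 6.2 no-go rule differs from the primary outcome because it includes a measurement that the protocol does not plan. As written, the rule cannot be applied without an unplanned choice. At a true flap-measurement success rate of 90%, that choice moves the chance of a no-go from about 0.02% to 100%. These figures assume 18 consenters and independence between women; the 100% also assumes that absent readings are scored as failures.

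The fault is in the wording of a primary decision rule, not in the design, the sample size or the thresholds. It should be corrected before the feasibility verdict is drawn.

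**What to change.** In section 6.2, replace the reference to flap and peri-incisional temperatures with the section 4.1 definition: success means that all flap temperatures were obtained in four quadrants at pre-mastectomy, post-mastectomy and pre-implant, for each relevant breast. Keep the 65% floor.

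If peri-incisional readings are in fact wanted, define their site, time points and number, and add them to sections 2.1, 4.1, 5.1, Table 1, 6.1 and 6.3. That would change the primary outcome and needs its own justification.

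The first option is a change of wording only, with no new data, staff or patients. It does not settle a separate mismatch in the same sentence: 11/18 = 61.1% is below 65% but is not fewer than 11. The percentage and the count should be aligned in the same edit.

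### Section 6.2: each feasibility limit gives a percentage and a count that differ by one patient (for measurement, if 18 consent), and the 19.4-point precision applies to consent only

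*Combined protocol and SAP*

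**What the plan says.** Section 6.2 (Sample Size) plans for 30 eligible patients and says "An n of 30 will provide reasonably tight estimates of our parameters of interest". It continues: "We will be able to estimate these proportions within 19.4% (for the lower CI bound", adding that the upper window is smaller and that the interval is two-sided at 95%.

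It then sets two lower limits. For consent: "If the consent proportion is below 40.6% (fewer than 12 women consenting out of the 30 eligible". For complete measurement: "fewer than 65% of the expected n=18 (i.e., fewer than n=11 women out of the starting pool of 30". If either is crossed, "we will conclude that a larger study of flap temperatures may not be feasible".

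The denominator for measurement success is given elsewhere as the women who consent. The hypotheses at the end of section 1.0 speak of success "at each time point on at least 90% of those who do consent", section 6.1 says "we will successfully measure all relevant temperatures (12 per breast) on at least 90% of those consenting", and section 6.3 likewise refers to patients who have consented. On the 60% and 90% targets, section 6.1 says "Both of these measures must be achieved to deem a future study feasible".

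**The concern.** A limit written two ways should give the same answer for every possible result. Here neither does, and nothing in the document says which form governs. At exactly 12 of 30 consenting, or 11 of 18 fully measured, one form triggers the negative feasibility statement and the other does not, so the choice could be made after the data are seen.

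The measurement count is also described by reference to the 30 eligible women, although its denominator is the consenters. It is therefore unclear whether 11 is a fixed count or only the equivalent of 65% of 18.

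The precision sentence has a related problem. It attaches one figure, based on 30, to both primary proportions, although the second is expected to rest on 18. A reader judging whether the sample is adequate would take the measurement estimate to be more precise than it will usually be.

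**Working it through.** **Inputs.** 30 eligible; 60% consent, so 18 consenters; 90% success among consenters (16.2, nearest whole number 16); two-sided 95% interval; limits of 40.6% or 12, and 65% or 11. The targets are in section 6.1 and the rest in section 6.2.

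**Reproducing the plan's figures.** The exact (Clopper-Pearson) limits for x of n are L = Beta⁻¹(0.025; x, n−x+1) and U = Beta⁻¹(0.975; x+1, n−x). For 18/30, L = 40.6% and U = 77.3%, so the distances are 60.0 − 40.6 = 19.4 below and 77.3 − 60.0 = 17.3 above. This matches the 19.4, the 40.6% and the remark about the upper side. Other methods do not match (points below: Wald 17.5, Wilson 17.7, Agresti-Coull 17.7, Jeffreys 17.8). For 16/18, L = 65.3%, which is evidently the source of the 65%.

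**Consent limit.** 0.406 × 30 = 12.18, so the percentage is crossed by 12 or fewer. The text says fewer than 12, which is 11 or fewer. The conflict is at 12/30 = 40.0%. The denominator is fixed at 30, so this holds without any condition.

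**Measurement limit.** 0.65 × 18 = 11.7, so with 18 consenting the percentage is crossed by 11 or fewer. The text says fewer than 11, which is 10 or fewer. The conflict is at 11/18 = 61.1%. In both cases the product appears to have been cut down to a whole number and then combined with a strict inequality.

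If 11 is read as a fixed count, it matches 65% only when 16 consent. The smallest number of successes reaching 65% is:

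| Consenters | 15 | 16 | 17 | 18 | 19 | 20 |
|---|---|---|---|---|---|---|
| Successes needed | 10 | 11 | 12 | 12 | 13 | 13 |

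**Precision for measurement success (exact method).**

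| Result | 95% interval | Points below estimate |
|---|---|---|
| 15/18 | 58.6% to 96.4% | 24.8 |
| 16/18 | 65.3% to 98.6% | 23.6 |
| 17/18 | 72.7% to 99.9% | 21.7 |
| 18/18 | 81.5% to 100% | 18.5 |
| 27/30 | 73.5% to 97.9% | 16.5 |

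With 18 consenting and true success 90%, the lower distance averages 22.7 points. It exceeds 19.4 in every likely result except 18/18, so the chance of exceeding it is 1 − 0.9¹⁸ = 1 − 0.150 = 85%. The 19.4 is not the measurement figure on either denominator. The section's own 65% limit against a 90% target already implies 90 − 65 = 25 points.

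**How often the two forms disagree.** I enumerated all results, with consenters ~ Binomial(30, 0.6) and successes ~ Binomial(consenters, 0.9), reading 11 as a fixed count. The count form passes in 98.0% of trials and the percentage form in 97.6%; they disagree in 1.55%. Exactly 12 consenting has probability 1.29%. It produces a disagreement only if at least 11 of those 12 are fully measured (0.9¹² + 12 × 0.1 × 0.9¹¹ = 0.659), so it contributes 0.0129 × 0.659 = 0.85 points of the 1.55.

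The rate rises when feasibility is in doubt: about 7% at 50% consent and 90% success, and about 19% at 60% and 70%. Taking each limit alone:

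| Limit and true rate | Crossed by count | Crossed by percentage |
|---|---|---|
| Consent, 50% | 10.0% | 18.1% |
| Consent, 60% | 0.8% | 2.1% |
| Measurement (18 consenting), 70% | 14.1% | 27.8% |
| Measurement (18 consenting), 80% | 1.6% | 5.1% |

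**Can a disagreement meet the section 6.1 targets?** No, whatever the true rates. A disagreement needs 12 consenters, or at least 11 successes that are still under 65% of consenters, or 10 or fewer successes that reach 65%. The last requires at most 15 consenters, since 10/16 = 62.5%. Each case misses the 60% or the 90% target.

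**The case against.** The best case on the other side is about weight. Section 6.1 sets the condition for calling a future study feasible, and 12/30 or 11/18 fails it under either form. Section 6.2 adds only a softer negative statement. Section 6.3 will report a confidence interval and a binomial test for each measure, and none of those change. All of this stands, and it keeps the point small.

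It can also be said that 11 is introduced as a gloss on 65% of 18, so a proportional reading is natural and the mention of 30 may only say where the women come from. That is fair. It weakens the fixed-count comparison at other numbers of consenters, but it does not remove the conflict at 18, the case the text itself names.

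On precision, the 19.4 can be seen as a loose summary that the next sentence corrects in effect, by naming 18 women and a 65% limit. A careful reader could work that out. But the sentence rests on a sample of 30 and covers both proportions in the plural, so as written it is wrong for the second. With a denominator of 30 a bound of 19.4 would hold near 90% (16.5 at 27/30); with 18 it usually does not.

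**Conclusion.** The point holds. The consent percentage and count differ by one patient unconditionally. The measurement percentage and count differ by one patient if 18 consent. The 19.4-point precision is correct for consent at 18/30 by the exact method; for measurement success at the expected denominator the figure is about 24 points at 16/18, and 19.4 is exceeded in 85% of outcomes if true success is 90%.

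The practical effect is small under the planning values: about 1.6% of trials give conflicting answers on the fixed-count reading, and none of these meets both section 6.1 targets. The 1.6% should not be carried over to lower true rates, where it rises to about 7% or 19% in the settings shown. The underlying bounds of 40.6% and 65% are sound. The errors lie in the counts and in applying one precision figure to both measures. This should be fixed, because these are the plan's lower feasibility limits and its only stated precision for the two primary measures.

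**What to change.** Have the sponsor state which form governs, then align the other.

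- **If the percentages govern** (they track the exact lower bounds for 18/30 and 16/18): give the consent limit as fewer than 13 of the 30 eligible. Give the measurement limit as fewer than 65% of consenting women, that is, fewer than 12 if 18 consent, and remove the reference to the pool of 30.
- **If the counts govern:** change the percentages to 40.0% and 61.1%, and state that the second count assumes 18 consenting.

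In either case, limit the 19.4-point statement to consent and name the exact method. Add that measurement success will have about 24 points below the estimate if 18 consent (16/18: 65.3% to 98.6%).

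While editing the paragraph, the sponsor should confirm whether its mention of peri-incisional temperatures is a leftover, since sections 4.1, 6.1 and 6.3 define success by flap readings alone.

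The cost is wording only, with no change to sample size or procedures. Under the first option each count becomes one patient stricter. Under the second the stated percentages fall by 40.6 − 40.0 = 0.6 and 65 − 61.1 = 3.9 points. The stated precision for measurement becomes less favourable.
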